2.2. Study Rationale

Raxibacumab was approved for the treatment of inhalation anthrax by the FDA on December 14, 2012 under the Animal Efficacy Rule per the U.S. Code of Federal Regulations (CFR) (21 CFR § 314.610). Raxibacumab is a fully human monoclonal IgG₁λ antibody (Ab) which binds the protective antigen (PA) component of the tripartite anthrax toxin, thus blocking the deleterious effects of lethal toxin and edema toxin.

Raxibacumab may be administered for prophylaxis of inhalation anthrax when alternative therapies are not available or are not appropriate. Anthrax Vaccine Adsorbed (AVA, BioThrax) which is mainly composed of adsorbed PA, may also be administered as part of a prophylaxis regimen. Published results indicate that a polyclonal anti-PA antitoxin administered to rabbits with AVA resulted in essentially complete abrogation of the immune response to AVA [Malkevich, 2013]. Since the primary antigen in AVA is PA, it is possible that concurrent administration of AVA and raxibacumab would result in raxibacumab binding the PA from AVA, leading to a reduced immune response to the vaccine and decreased anti-PA Ab concentrations and toxin neutralizing activity (TNA) titers. This study, as a post-marketing commitment to the FDA, is designed to detect the effect of raxibacumab on AVA immunogenicity in a healthy volunteer population.

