9.2. Sample Size Considerations

9.2.1. Sample Size Assumptions

The sample size calculation is based on the assumption that the individual values will be analyzed after being transformed by \log_{10} resulting in data that is approximately normal. In the transformed data the analysis of the ratio of the means is equivalent to a difference of mean values with a margin of $\log_{10}(1.5) = 0.176$.

The standard deviation of the \log_{10} transformed data is assumed to be 0.75. This is selected based on the fact that the sample size in [Marano et al. \(2008\)](#) was based on a standard deviation of 0.45 based on the data from [\[Pittman, 2002\]](#), but the results from the [Marano et al. \(2008\)](#) study had higher standard deviations suggesting an estimate closer to 0.85.

The sample size is calculated assuming 1:1 randomization and two interim analyses for futility after 30 and 100 analyzable subjects. The boundaries for the futility analysis are based on Rho family error spending function with a rho of 0.5. For the purposes of the sample size calculation, the power will be calculated under the alternative hypothesis setting, where the ratio is 1, or equivalence between the two arms with respect to concentrations of anti-PA antibody. With a type 1 error of 5% one-sided a sample size of 534 subjects will allow for 80% power to make a claim of non-inferiority (margin of 1.5), if the true ratio between the geometric means is 1. In a trial of 534 patients, the largest observed GMC ratio between the AVA and the combination that results in a statistically significant non-inferiority result is an estimated ratio of 1.173. This can alternatively be viewed as a minimum observed anti-PA concentration due to the addition of AVA in the combination of ~85% of the concentration when AVA is administered alone. This is under the assumption that the observed variability in the study population is similar to the study design assumption.

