At the first interim the confidence interval for the ratio will be based on a t statistic with 28 degrees of freedom (for instance for a 90% CI the relevant t value is $t_{.05,28}=1.701$). The exact precision of the estimate will be dependent on the observed sample estimate of the standard deviations. Assuming both treatment groups have a sample standard deviation equivalent to the assumed 0.75, the assumed standard error would be 0.274. The 90% confidence interval will vary by $\pm .466$. Translated back to the original scale, the GMC ratio will be scaled by .342 or 2.92.

For the second interim, the assumed standard error in the log transformed data would be .15. The 90% confidence interval would vary by $\pm .249$ in the log transformed data and scaled 0.564 or 1.775 in the original scale GMC ratio.

At the final analysis, the assumed standard error in the log transformed data would be .065. The 90% confidence interval would vary by $\pm .107$ in the log transformed data and scaled by 0.782 or 1.28 in the original scale GMC ratio.

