9.4. Key Elements of Analysis Plan

9.4.1. Primary Analyses

At the final analysis, the non-inferiority test will be based on a comparison of the CI for the ratio of anti-PA Ab (attributable to AVA) GMCs between the AVA and the AVA + raxibacumab groups at week 4. This analysis will be performed in the per protocol population. If the upper bound of the 90% CI is less than 1.5, non-inferiority will be established.

This analysis will be repeated in the subset of the intent-to-treat population with available week 4 results, as a sensitivity analysis. Another set of sensitivity analyses will use the full ITT population with imputation for subjects without week 4 anti-PA Ab concentration results. The first imputation will be as follows: In the AVA + raxibacumab arm, missing data will be imputed with the first quartile from the non-missing data in this arm. In the AVA arm, missing data will be imputed with the third quartile from the non-missing data in this arm. The second imputation will be as follows: In the AVA + raxibacumab arm, missing data will be imputed with the lower limit of quantitation (LLQ). In the AVA arm, missing data will be imputed with the maximum from the non-missing data.

The GMCs for each treatment group will be summarized along with the 95% confidence intervals for the week 4 timepoint as well as weeks 8 and 26.

The GMC ratio and GMCs within each cohort and corresponding CIs will be calculated by first log transforming all of the data by a log base 10. A t-test will be performed and CIs will be calculated about the mean logs and the difference of the mean logs. The results will be translated back to the original scale by exponentiating them, again using a base 10. The exponentiated differences of the sample mean logs will be the ratio of the sample geometric means of the untransformed results.

Sensitivity analyses will be performed to assess the sensitivity of the results to the assumption of equality of variances between the anti-PA Ab concentrations in the two treatment groups. Details will be described in the analysis plan.

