4.9 Interim Analyses

Two interim analyses are scheduled to allow early termination of the study if a large effect of raxibacumab on AVA immunogenicity is confirmed at the interim. The first interim analysis will be performed after at least 30 analyzable subjects have reached the Week 4 endpoint. The trial is randomizing 34 patients to ensure that at least 30 subjects are analyzable, so it is possible that there will be more than 30 patients analyzed in the first interim. The second interim will be performed after the first 100 analyzable subjects have reached the Week 4 endpoint. There may also be additional subjects randomized to meet the total of 100 analyzable subjects for the second interim. The final number enrolled will be informed by the level of drop-outs observed in the first 34 subjects randomized.

These interim analyses will be performed on the per-protocol population by independent unblinded statistical and medical personnel using unblinded data.

For the interim analyses, the immunogenicity data will be summarized by the ratio of geometric mean concentrations (GMC) of anti-PA antibody levels with corresponding 95% CI. A two sample t-test for the log transformed data will be performed and a corresponding p-value will be provided which will be used to determine if the futility threshold has been crossed at the respective interim analyses. No imputations will be utilized for interim analyses. The study will be terminated early if the futility boundary is crossed at an interim, otherwise, recruitment for next phase will begin.

The futility thresholds for the interim analyses will be based on a rho (0.5) type II error spending function. The t-statistics for the boundaries, as calculated in East 5.4, are 1.0274 for interim 1 (sample size = 30 subjects), 0.4437 for interim 2 (sample size = 100 subjects) and -1.645 for the final analysis. These correspond to p-values for the t-test of p=0.848 at interim 1, p=0.671 at interim 2, and p=0.05 for the final analysis.

Note: The futility boundary will be recalculated by the unblinded statistician based on the actual number of subjects who comprise the primary analysis population for cohort 1. These boundaries will be calculated using East 6.2.

For these interim analyses, the results will include:

- calculations of futility boundaries (Table 14.2.3.1.1);
- a summary of statistical comparison of anti-PA antibody levels (Table 14.2.3.1.2);
- a demographic summary (Table 14.1.2);

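### The planned CIs for the GMC ratio ignore the two futility stops, so the lower limit reported where the trial ends misses its nominal level when the true ratio is near 1

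*Protocol*

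**What the plan says.** Protocol 9.3.2 describes the interval at each of the three looks as a fixed-sample t-interval. For the first look, "At the first interim the confidence interval for the ratio will be based on a t statistic with 28 degrees of freedom", with 1.701 given as the example multiplier for a 90% interval. The 90% half-widths on the log10 scale are .466, .249 and .107 at 30, 100 and 534 subjects.

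Protocol 9.4.1 does the same at the final analysis: "A t-test will be performed and CIs will be calculated about the mean logs and the difference of the mean logs". The decision rule is "If the upper bound of the 90% CI is less than 1.5, non-inferiority will be established". SAP 4.11 repeats both.

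SAP 4.9 lists, as interim output, the "ratio of geometric mean concentrations (GMC) of anti-PA antibody levels with corresponding 95% CI", and ends the study if the futility boundary is crossed.

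Neither document provides an interval or estimate adjusted for the sequential design. Neither warns that an estimate taken after a futility stop is biased. Protocol 9.3.2 says only that the interim estimates will be imprecise.

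**The concern.** The trial can stop early in one direction only, when the observed ratio is high. The interval from the stopping look is then the one that gets reported. The upper limit is protected, because non-inferiority can be claimed only at the last look. The lower limit has three chances to land above the true ratio, and an ordinary t-interval does not account for that.

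The study is described as "designed to detect the effect of raxibacumab on AVA immunogenicity in a healthy volunteer population". After a futility stop, readers will look to the ratio and its lower limit to judge whether raxibacumab interferes with AVA and by how much at least. If that limit is too high too often, interference is overstated.

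**Working it through.** **Inputs.** Protocol 9.2.1: "With a type 1 error of 5% one-sided a sample size of 534 subjects will allow for 80% power"; the SD of the log10 "transformed data is assumed to be 0.75"; power taken "where the ratio is 1, or equivalence between the two arms"; 1:1 allocation; looks at 30, 100 and 534 analyzable subjects. Protocol 9.3.2: futility boundaries 1.0274 and 0.4437 for the t-statistic against the margin, and -1.645 at the end. Margin: log10(1.5) = 0.176.

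**Step 1: reproduce the plan's figures.** With n per arm of 15, 50 and 267, SE = 0.75 × √(2/n) = 0.274, 0.150 and 0.0649.
- Cutoffs on the ratio scale: 10^(0.176 + 1.0274 × 0.274) = 2.87 and 10^(0.176 + 0.4437 × 0.150) = 1.75. Success at the end: 10^(0.176 − 1.645 × 0.0649) = 1.173. All match.
- Simulating the three-look design (pooled-variance t, 2,000,000 trials, true ratio 1) gives stops of 5.0% and 3.9% and power 79.8%. Protocol 9.2.2, Table 5, gives 4.9%, 3.8% and 80%.

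**Step 2: why the lower limit is affected.** The protocol's log10 stopping cutoffs are .4575 and .242. Its 90% half-widths at those looks are .466 and .249, almost the same. A trial that stops will therefore usually have a 90% interval that excludes 1, even when the true ratio is 1. The 95% half-widths are 2.048 × 0.274 = 0.561 and 1.984 × 0.150 = 0.298, or ratios of about 3.64 and 1.98. At a true ratio of 1, the geometric-mean observed ratios among stopped trials are about 3.6 and 2.0, so roughly half of those 95% intervals exclude 1.

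**Step 3: coverage at the look where the trial ends, true ratio 1, SD 0.75.**

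| Levels used | Lower limit above truth: interim 1 + interim 2 + final | Upper limit below truth | Coverage |
|---|---|---|---|
| SAP: 95%, 95%, 90% | 2.49 + 1.67 + 3.66 = 7.8% | 4.9% | 87.3% |
| 90% at every look | 4.63 + 3.46 + 3.66 = 11.7% | 4.9% | 83.3% |
| 95% at every look | 2.49 + 1.67 + 1.73 = 5.9% | 2.5% | 91.6% |

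For the SAP mix, 8.87% of trials stop early and 91.13% reach the end. The nominal benchmarks are therefore 0.0887 × 95 + 0.9113 × 90 = 90.4% coverage and 0.0887 × 2.5 + 0.9113 × 5 = 4.8% lower-side error. With the SAP's 95% interval, about half of the interim 1 stops and 43% of the interim 2 stops exclude 1. With no stopping rule, the 90% interval covers 90.0%, so the shortfall comes from the stopping rule.

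**Step 4: other true ratios.**

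| True ratio | 90% at every look: coverage (lower-side error) | SAP levels: coverage |
|---|---|---|
| 1 | 83.3% (11.7%) | 87.3% |
| 1.5 | 87.1% (8.5%) | 90.7% |
| 2 | 90.3% (6.5%) | 93.4% |
| 4 | 91.8% (5.0%) | 96.0% |
| 10 | 91.5% (4.9%) | 96.1% |

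With 90% at every look, coverage is 83.8% at ratio 1.11 and 85.0% at 1.25. At ratio 1 it is 83.4% if the SD is 0.9, and 83.6% if 34 subjects are analyzed at interim 1.

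**Step 5: the adjusted lower limit.** Choose c so that the largest of three standard normal statistics, with correlations √(n_i/n_j) (0.548, 0.237 and 0.433), exceeds c with the required one-sided probability.
- For 5%: c = 2.076, or 1.89% per look. The t multipliers are 2.179, 2.105 and 2.081, and the lower scale factors are 10^(−2.179 × 0.2739) = 0.253, 10^(−2.105 × 0.150) = 0.483 and 10^(−2.081 × 0.0649) = 0.733. The protocol's present factors are 0.342, 0.564 and 0.782.
- For 2.5%: c = 2.359, or about 0.92% per look. The multipliers are 2.506, 2.400 and 2.367, and the factors are 0.206, 0.437 and 0.702.

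With the 90% version and the upper limit left alone, lower-side error at ratio 1 falls from 11.7% to about 4.4%. Coverage is at least 90% at every ratio tried from 0.8 to 10.

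**The case against.** The strongest reply is that nothing the trial formally decides uses the lower limit. The only hypothesis is one-sided non-inferiority at 1.5, settled by the upper limit. No section treats an interval wholly above 1 as proof of interference. This stands. The false-claim rate at ratio 1.5 is 4.4%, and trials that reach the final analysis at ratio 1 have 90.6% coverage. A reader might infer that the non-inferiority test is compromised; the documents and the calculation do not support that.

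A reader might also take 83% coverage, with more than double the nominal lower-side error, as the plan's own performance. That requires a 90% interval at every look. Protocol 9.3.2 gives 90% at the first look only as an example, in a discussion of precision, while SAP 4.9 specifies 95% at the interims. The figure for the SAP's levels is about 87%.

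Nor can the shortfall be tied to the outcome the sponsor expects. Early stops are likely when the true ratio is large, and there coverage is adequate. At ratio 1, Table 5 puts the chance of an early stop at 8.7%, a risk the protocol discloses and accepts.

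What the reply does not remove is that intervals will be reported at a stated confidence level they do not have near a ratio of 1, always erring toward interference. The protocol's caution about imprecision concerns width, not this.

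The repeated interval also has limits. It is conservative (about 94% to 95% coverage at ratios of 2 or more) and widens the final-look lower side, where coverage at ratio 1 is already 90.6%. It leaves the point estimate uncorrected. At ratio 1, its 90% version still excludes 1 in 38% of interim 1 stops and 31% of interim 2 stops. It should therefore accompany the ordinary interval, not replace it.

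**Conclusion.** The point holds as a reporting defect. With the SAP's interval levels, a true ratio of 1 and SD 0.75, coverage at the look where the trial ends is about 87%, against a weighted nominal 90.4%. The lower limit exceeds the truth in 7.8% of trials, against 4.8%. The range across interval levels is 83% with 11.7% (90% throughout, nominal 5%) to 91.6% with 5.9% (95% throughout, nominal 2.5%).

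The shortfall is confined to true ratios below about 1.5 to 2. The upper limit, boundaries, power and non-inferiority rule are unaffected.

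These figures assume normal log10 data with equal SDs, looks at exactly 30, 100 and 534, a boundary that is obeyed when crossed, and reporting of the interval from the look where the trial ends.

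**What to change.** Leave the ordinary interval and its upper limit in place for the non-inferiority decision. In protocol 9.3.2 and 9.4.1 and SAP 4.9 and 4.11:

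1. State that the ordinary interval after a futility stop is not adjusted for the stopping rule, and that the observed ratio is then biased toward interference.
2. Report beside it a repeated-confidence-interval lower limit for looks at 30, 100 and 534. Use about 0.92% one-sided per look for a 95% interval, or about 1.9% for a 90% interval (scale factors 0.253, 0.483 and 0.733 at SD 0.75). Fix one level in advance for all three looks, and recompute the per-look level if the analyzed numbers differ, as SAP 4.9 already does for the futility boundary.
3. Base any statement that interference exists, or about its minimum size, on that adjusted limit.

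The cost is wording and one extra reported limit, which is wider and somewhat conservative. No subjects are added, and the boundaries, power and decision rule stay as they are.

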9.4. Key Elements of Analysis Plan

9.4.1. Primary Analyses

At the final analysis, the non-inferiority test will be based on a comparison of the CI for the ratio of anti-PA Ab (attributable to AVA) GMCs between the AVA and the AVA + raxibacumab groups at week 4. This analysis will be performed in the per protocol population. If the upper bound of the 90% CI is less than 1.5, non-inferiority will be established.

This analysis will be repeated in the subset of the intent-to-treat population with available week 4 results, as a sensitivity analysis. Another set of sensitivity analyses will use the full ITT population with imputation for subjects without week 4 anti-PA Ab concentration results. The first imputation will be as follows: In the AVA + raxibacumab arm, missing data will be imputed with the first quartile from the non-missing data in this arm. In the AVA arm, missing data will be imputed with the third quartile from the non-missing data in this arm. The second imputation will be as follows: In the AVA + raxibacumab arm, missing data will be imputed with the lower limit of quantitation (LLQ). In the AVA arm, missing data will be imputed with the maximum from the non-missing data.

The GMCs for each treatment group will be summarized along with the 95% confidence intervals for the week 4 timepoint as well as weeks 8 and 26.

The GMC ratio and GMCs within each cohort and corresponding CIs will be calculated by first log transforming all of the data by a log base 10. A t-test will be performed and CIs will be calculated about the mean logs and the difference of the mean logs. The results will be translated back to the original scale by exponentiating them, again using a base 10. The exponentiated differences of the sample mean logs will be the ratio of the sample geometric means of the untransformed results.

Sensitivity analyses will be performed to assess the sensitivity of the results to the assumption of equality of variances between the anti-PA Ab concentrations in the two treatment groups. Details will be described in the analysis plan.

9.4.2. Secondary Analyses

9.4.2.1. Anti-PA Antibodies

Anti-PA antibody concentrations will also be collected at weeks 8 and 26 after the first AVA dose. The GMCs along with 95% CI will be summarized for each treatment group at each timepoint. There will be no imputation for subjects with missing data at a given timepoint.

9.4.2.2. Toxin Neutralizing Activity (TNA)

TNA titers will be collected at weeks 4, 8 and 26 after the first AVA dose. The GMTs along with 95% CI will be summarized for each treatment group at each timepoint. There will be no imputation for subjects with missing data at a given timepoint.

The percentage of subjects, along with 95% CI, who seroconvert, defined as a >4-fold increase in toxin neutralizing activity (TNA) titer will be summarized, at Weeks 4, 8 and 26 after the first AVA dose for both arms separately.

9.4.2.3. Safety Analyses

Clinical safety observations will include AEs, urinalysis, vital sign measurements, and clinical laboratory assessments. Safety data will be tabulated and, where appropriate, analyzed by the use of descriptive statistics. Safety data will be tabulated for the Safety Population.

The number (%) of subjects withdrawing from the study will be summarized for each treatment group and the number (%) subjects withdrawing for each individual reason will be summarized by treatment group.

Reported AEs will be coded using MedDRA. The number (%) of subjects in each treatment group with treatment-emergent AEs will be compared for overall incidence and by system organ class and preferred term. Similar summaries will also be presented for deaths, all SAEs, AEs leading to withdrawal, and drug-related AEs. Severity of treatment-emergent AEs will also be summarized by system organ class, preferred term, and treatment group.

Additionally, the frequency of laboratory abnormality events along with shifts from baseline will be summarized, as well as changes over time in laboratory parameters, urinalysis and vital signs.

